6.2 Evaluation and Response

6.2.1 For Groups A, B, C, and D:

- PET-CT scan and/or CT scan with intravenous/oral contrast of neck, chest, abdomen and pelvis will be performed for response evaluation 90-100 days post ASCT, 180-200days post ASCT, 360-380 days post ASCT and 540-560 days post ASCT. Response criteria will follow the Lugano Classification (see Appendix B). Both PET/CT and CT scan should be done within 30 days prior to initiation of ASCT conditioning for baseline response evaluation purposes. Either PET/CT or CT scan are acceptable for response evaluation after ASCT, and should be compared to the pre-ASCT baseline scan.
- Physical exam, laboratory work-up and correlative studies will be performed as delineated in the Clinical Trial Flowchart (Appendix D)

Amendment9 09NOV2021 Page 32 of 77

6.2.2 For Groups E and F:

- Serum protein electrophoresis with immunofixation, quantitative serum IgG, IgM, IgA (IgE or IgD in cases where this is the involved immunoglobulin), serum free light chains, 24-hour urine for protein electrophoresis with immunofixation and protein quantification will be collected for response evaluation 30-40 days post ASCT, 60-70 days post ASCT, 90-100 days post ASCT, 180-200 days post ASCT, 270-290 days post ASCT, 360-380 days post ASCT, 450-470 days post ASCT and 540-560 days post ASCT. Response criteria will follow the International Myeloma Working Group (IMWG) Uniform Response Criteria for Multiple Myeloma (see Appendix C). For patients who achieve CR by IMWG Criteria, a bone marrow biopsy will be required for confirmation and tumor immunophenotype analysis
- Physical exam, laboratory work-up, and correlative studies will be performed as delineated in the Clinical Trial Flowchart (Appendix D)

6.2.3 For All Groups:

- If a patient signs consent but does not receive treatment, the patient will not be evaluable and no further safety information will be collected. The slot will be released and may be re-assigned to another patient.
- If there is progressive disease or relapse documented by any of the criteria, a confirmatory lymph node and/or bone marrow biopsy will be performed for confirmation of disease relapse and tumor immunophenotype studies.

7.0 DATA SAFETY MONITORING

The Georgetown Lombardi Comprehensive Cancer Center will be responsible for the data and safety monitoring of this multi-site trial. As this study is an investigator initiated Phase Ib/IIa study utilizing a non-FDA approved drug for this indication which the FDA has deemed IND-exempt, it is considered a high-risk study, which requires real-time monitoring, by the PI and study team and reviewed every 4 months by the LCCC Data and Safety Monitoring Committee (DSMC).

The Principal Investigator and the Co-Investigators will review the data including safety monitoring at their weekly institution based disease group meetings and on monthly disease group teleconferences.

All Severe Adverse Events (SAEs) are required to be reported to the IRB. Based on SAEs, the IRB retains the authority to suspend further accrual pending more detailed reporting and/or modifications to further reduce risk and maximize the safety of participating patients.

Progress on the trial and the toxicities experienced will be reviewed by the LCCC Data and Safety Monitoring Committee every 4 months from the time the first patient is enrolled on the study. Results of the DSMC meetings will be forwarded to the IRB with recommendations regarding need for study closure.

DSMC recommendations should be based not only on results for the trial being monitored as well as on data available to the DSMC from other studies. It is the responsibility of the PI to ensure that the DSMC is kept apprised of non-confidential results from related studies that become available. It is the responsibility of the DSMC to determine the extent to which this information is relevant to its decisions related to the specific trial being monitored.

A written copy of the DSMC recommendations will be given to the trial PI and the IRB. If the DSMC recommends a study change for patient safety or efficacy reasons the trial PI must act to implement the change as expeditiously as possible. In the unlikely event that the trial PI does not concur with the DSMC recommendations, then the LCCC Associate Director of Clinical Research must be informed of the reason for the disagreement. The trial PI, DSMC Chair, and the LCCC AD for Clinical Research will be responsible for reaching a mutually acceptable decision about the study and providing details of that decision to the IRB. Confidentiality must be preserved during these discussions. However, in some cases, relevant data may be shared with other selected trial investigators and staff to seek advice to assist in reaching a mutually acceptable decision.

If a recommendation is made to change a trial for reasons other than patient safety or efficacy the DSMC will provide an adequate rationale for its decision. If the DSMC recommends that the trial be closed for any reason, the recommendation will be reviewed by the Associate Director for Clinical Research at G-LCCC. Authority to close a trial for safety reasons lies with the IRB, with the above described input from DSMC and the AD for Clinical Research.

8.0 STATISTICAL CONSIDERATION

This is an open label, single-arm per cohort, phase lb-IIA study.

Our goal is to determine the safety and clinical effect of combined checkpoint inhibition administered after autologous hematopoietic stem cell transplantation in each of six clinical cohorts of high risk and recurrent disease. In addition to assessing the incidence and severity of adverse events and rates of complete response and progression free survival, we intend to monitor immune reconstitution, phenotype and TCR repertoire throughout treatment and at the time of disease progression. We will also analyze the gut microbiome prior to conditioning, throughout treatment, post-transplant and at time of relapse. We intend to expand cohorts that demonstrate safety and PFS >50% at 18 months into a phase IIA successor trial.

This is an open label, single-arm per cohort, phase Ib-IIA study.

Phase Ib

The primary objectives of this study are:

To assess the safety of combined check point inhibition with nivolumab and ipilimumab
after autologous hematopoietic stem cell transplantation in patients at high risk for posttransplant recurrence including patients with persistent and recurrent high risk diffuse
large B cell lymphoma, high risk and recurrent T cell lymphoma and high risk and recurrent
multiple myeloma.

Primary endpoints:

- Safety endpoint: The composite endpoint consisting of the occurrence of at least one
 treatment-related limiting toxicity (after combined checkpoint inhibitor treatment is
 initiated) defined as a ≥ grade 4 non-hematologic toxicity as specified by the CTCAE.
 Exceptions listed in section 5.9 apply to this endpoint as well. If 3 of 7 patients in a single
 cohort experience a treatment-related limiting toxicity, that single cohort will be terminated.
- Efficacy endpoint: progression-free survival at 18 months after ASCT in patients at high risk for post-transplant recurrence including patients with persistent and recurrent high risk diffuse large B cell lymphoma, high risk and recurrent T cell lymphoma and high risk and recurrent multiple myeloma.

The secondary objectives are:

- To assess complete response rate at 3, 6 and 12 months after ASCT in patients at high risk for post-transplant recurrence including patients with persistent and recurrent high risk diffuse large B cell lymphoma, high risk and recurrent T cell lymphoma and high risk and recurrent multiple myeloma.
- To assess progression-free survival at 12 months after ASCT in patients at high risk for post-transplant recurrence including patients with persistent and recurrent high risk diffuse large B cell lymphoma, high risk and recurrent T cell lymphoma and high risk and recurrent multiple myeloma.
- To assess blood immune reconstitution, phenotype and TCR repertoire at screening (at time of informed consent), at apheresis (stem cell collection), and then serially the day 1 of week 1 of combined checkpoint inhibitors and then weeks 4, 7, 12, 18 and 26, and at 9, 12, 15, and 18 months post-transplant and at time of relapse, as it occurs. Immune phenotype and TCR will be evaluated as follows:

T cell repertoire analysis

TCR Immunoseg for Vbeta CDR3 highest frequency specificities.

Real-Time PCR analysis:

T-bet(Th1); STAT3, RORgamma t (TH17); STAT6 (Th2); FoxP3 (Treg), granzyme A (GZMA) and perforin (PRF1)

Flow Cytometric Phenotype Analysis for:

T Cells:

CD3; CD4; CD8; CD4+CD25+PD1+; CTLA-4 Follicular Helper T: CD3+,CD4+,CXCR5+,PD1+ CD4 and CD8 T naïve (RO-; CCR7+) Central Memory: (TCM;RO+,CCR7+) Effector Memory (TEM, RO+,CCR7-)

Terminally differentiated effector memory (TEMRA; RO-, CCR7-)

T regulatory cells (Treg): CD4+,CD25hi, CD127low, CD39+, CD152hi, RO-(resting); CD4+,CD25hi, CD127low, CD39+, CD152hi, RO+ (activated)

Dendritic Cells:

Lin-, CD11c+, CD1a+, CD80 (B7-1)low, CD86 (B7-2)low, MHC Class Illow (DC resting); CD11c+, CD1a+, CD123-, CD80hi, CD86hi, HLADRhi (DC1 activated); HLADRhi, CD11c-, CD123+, PDL-1+ (DC2)

Macrophages:

HLADR+, CD14+, CD64+, CD25+, CCR7+ (M1); HLADR+, CD14+, CD64-, CD206+, CD25-, CCR7-, CD209+, PDL-1+ (M2)

Myeloid derived suppressor cells:

HLADR-/low, CD11b+, CD14+,CD33+hi,CD34+, CD66b-, PDL-1+ (M-MDSC); HLADR-, CD11b+, CD14-,CD33+low,CD34+, CD66b+, PDL-1+ (G-MDSC)

B Cells:

CD19+, B7-1low, B7-2low, MHC Class Illow (resting); CD19+, B7-1hi, B7-2hi, MHC Class Ilhi (activated)

Amendment9 09NOV2021 Page 35 of 77

NK cells:

CD16+, CD3-, CD56+

NKT Cells:

CD16+, CD3+, CD56+

Plasma Cytokine levels: Multiplex 25 Cytokine - Luminex

GM-CSF, IL-1b, IL-1RA, IL-2, IL-2R, IL-4, IL-5, IL-6, IL-7, IL-8, IL-10, IL-12, IL-13, IL-15, IL-17, TNF alpha; MCP-1, MIP1a, MIP1b, MIG, RANTES, IFN-alpha, IFN-gamma, IP-10, Eotaxin

- To determine the toxicities resulting from administration of the treatments.
- To assess tumor site immune phenotype, T cell repertoire and PD L1/2 expression when tissue available for biopsy prior to autologous transplant conditioning and then at time of progression (within 18 months) after autologous transplant conditioning.

The tertiary objectives are:

• To identify specific intestinal microbial strains associated with improved outcome in autologous stem cell transplantation patients treated with combined checkpoint inhibitors. The overall microbial composition in stool samples of patients will be analyzed at screening, preconditioning (to be collected within 48 hours prior to transplant admission), at engraftment (within 72 hours of ANC ≥ 500), and then serially, on day 1 of week 1 (to be collected within 48 hours prior to clinic visit) and then weeks 4, 7, 12, 18, and 26, End of Treatment, and 9, 12, 15 and 18 months post-transplant, and at time of relapse, as it occurs. A 16S ribosomal RNA (rRNA) miSeq Illumina platform will be used for overall microbial composition and quantitative real-time PCR analysis will validate the specific microbial strains identified by miSeq.

Phase IIA

Primary Objective

• To assess progression-free survival at 18 months after ASCT in patients in cohorts that were deemed safe in Phase Ib (no more than 3 treatment-related toxicity) and at least 4 of 7 patients progression free at 18 months in the Phase Ib.

Secondary Objectives

- To assess complete response rate at 3, 6 and 12 months after ASCT in patients at high risk for post-transplant recurrence including patients in the successor expansion cohorts following the Phase Ib trial.
- To assess progression-free survival at 12 months after ASCT in patients at high risk for post-transplant recurrence including patients with in the successor expansion cohorts following the Phase Ib trial.
- Determine the toxicities resulting from administration of the treatments in patients enrolled in the successor expansion cohorts following the Phase Ib trial.
- To assess blood immune reconstitution, phenotype and TCR repertoire at screening (at time of informed consent), at apheresis (stem cell collection), and then serially the day 1 of week 1 of combined checkpoint inhibitors and then weeks 4, 7, 12, 18 and 26, and at 9, 12, 15, and 18 months post-transplant and at time of relapse, as it occurs.

Tertiary Objectives

• To identify specific intestinal microbial strains associated with improved outcome in autologous stem cell transplantation patients treated with combined checkpoint inhibitors.

The overall microbial composition in stool samples of patients will be analyzed at screening, preconditioning (to be collected within 48 hours prior to transplant admission), at engraftment (within 72 hours of ANC \geq 500), and then serially, on day 1 of week 1 (to be collected within 48 hours prior to clinic visit) and then weeks 4, 7, 12, 18, and 26, End of Treatment, and 9, 12, 15 and 18 months post-transplant, and at time of relapse, as it occurs.

8.1 Determination of Sample Size

- The Phase Ib feasibility trial will require 42 patients divided in 6 cohorts, with 7 patients each. Enrolled patients will have hematologic malignancies with a high risk for post-autologous stem cell transplant recurrence including patients with persistent and recurrent high risk diffuse large B cell lymphoma, high risk and recurrent T cell lymphoma and high risk and recurrent multiple myeloma.
- The Phase IIA will require up to 148 patients, assuming all cohorts followed in Phase Ib meet the criteria for expansion.

Accrual goal is 7 patients per cohort. Accrual period goal is 36 months. Patients will accrue to study by disease groups (cohorts) and followed separately by group for incidence and severity of toxicity, ability to receive intended schedule of combined checkpoint inhibitors and for complete response and progression free survival (PFS) rates. Complete response and progression free survival rates will be compared to published standards for each disease group. Expected PFS at 18 months (PFS18) for all post-transplant groups without checkpoint inhibitors is 40-50%¹⁻³. Groups A, B, C, and D with PFS at 18 months in 4 or more patients (57%) will be considered for eligibility in a successor phase IIa expansion trial. The primary efficacy endpoint of the phase Ib portionis to achieve PFS of 18 months in ≥4 patients per cohort (≥57%).

Phase Ib

The initial part of the trial titled is designed as a feasibility Phase Ib study. This will determine which of 6 cohorts of patients would be studied in an expansion Phase IIa trial. In this pilot feasibility study, designed to assess the safety of the combined checkpoint inhibitor, sample size was not performed to estimate power, as it was designed to obtain initial estimates of toxicity to inform the successor trial Phase IIA. Therefore, this pilot feasibility study is not powered to detect significant differences in PFS. We have preemptively established a cut-off of ≥57% PFS at 18 months as the minimum benefit needed to proceed to Phase IIa for each individual cohort, if a maximum of 3 patients in each cohort experience severe adverse events which would lead to trial discontinuation (for that particular cohort). Historical data for such patient populations predicts PFS 40-50% at 18 months.

Phase IIa

8.2 Populations for Analysis

- The All-Subjects-as-Treated (ASaT) population will be employed for safety analyses. Descriptive tables that summarize the number and percentage of subjects that experience adverse events as categorized in the NCI CTCAE Version 4.03 will be generated by cohort/group.
- The intent-to-treat (ITT) population will be employed for response and PFS analyses.
 Descriptive tables that summarize the number and percentage of subjects with responses and PFS will be generated by cohort/group.

8.3 Statistical Methods

8.3.1 Safety Analysis

The safety of combined checkpoint inhibition with nivolumab and ipilimumab, after autologous hematopoietic stem cell transplantation in patients at high risk for post-transplant recurrence, will be evaluated for composite endpoint (at least one treatment-related toxicity and all adverse events observed in each cohort and presented as counts (percentages) and corresponding exact binomial 95% confidence intervals for proportion. Adverse events will include Immune-mediated colitis, hepatitis, endocrinopathies, nephritis, rash, encephalitis and immune-related AEs (irAEs).

8.3.2 Complete Response Rate

Complete response rate will be evaluated at 3, 6 and 12 months after ASCT in each of the 6 cohorts. The estimates of the CR will be presented as count (proportion) and corresponding exact binomial 95% confidence intervals for proportion at each time point.

8.3.3 Progression Free Survival at 12, 18 months

Progression-free survival (PFS) is defined as time interval from date of transplantation to pathologic disease progression or death from any cause. PFS of patients at high risk for post-autologous stem cell transplant recurrence in each cohort will be estimated using Kaplan-Meier method and probabilities will be calculated for months 12 months and 18 months, along with 95%. In Phase II, if PFS18 is at least 52% then study will have demonstrated the early efficacy that was sought in that particular cohort, i.e. PFS18 ≥ 57%.

8.3.4 Longitudinal analysis of TCR repertoire and blood immune phenotype

Longitudinal analysis of TCR repertoire analysis results reported as diversity scores will be conducted on samples as determined by DNA sequencing and analyzed by ImmunoSeq software (Adaptive Biotechnologies). TCR repertoire diversity scores in evaluable patient samples will be over time using mixed model repeated measures (MMRM) by utilizing PROC MIXED SAS 9.4. In this models, the status of infection as a time-dependent will be included to examine the effect of both time and infection on cell cytokine levels.

Longitudinal analysis will be performed on blood samples collected at 14 time points:

- 1) Screening Visit (at time of informed consent)
- 2) Apheresis Sample (except for group F, due to stem cell collection having occurred previously). For those patients who sign informed consent after apheresis has already occurred, the Apheresis Sample will be performed on the previously collected, frozen product.
- 3) Day 1 of Week 1 of combined checkpoint therapy,
- 4) Day 1 of Week 4 of combined checkpoint therapy,
- 5) Day 1 of Week 7 of combined checkpoint therapy,
- 6) Day 1 of Week 12 of combined checkpoint therapy,
- 7) Day 1 of Week 18 of combined checkpoint therapy, and
- 8) Day 1 of Week 26 of combined checkpoint therapy.
- 9) End of Treatment Visit
- 10) Post-transplant, 9 months,
- 11) Post-transplant, 12 months,
- 12) Post-transplant, 15 months.
- 13) Post-transplant, 18 months and / or
- 14) Relapse, as it occurs.

Cell counts in all subsets will be analyzed as repeated measurements obtained at the 14 timepoints to examine the changes over time or less when time of relapse as the last timepoint. This longitudinal analysis will be performed by fitting an overall model across subsets of cells and a separate longitudinal analysis within each subpopulation.

1. Overall model

Using all subsets, T cells, (T cells (CD4 versus CD8, Tregs, memory (central versus effector versus terminally differentiated effector memory), dendritic cells, macrophages, myeloid suppression cells, B cells, NK cells, NKT cells, analysis of cell counts will be performed to examine changes in counts over time (14 time points) and difference in counts between levels

Amendment9 09NOV2021 Page 39 of 77

of their state, naïve versus activated, as appropriate. The covariates in this model will be timepoints (14 timepoints listed above) and subset of cell population.

- 2. Within each subset, the following separate longitudinal analysis of cell counts over time will conducted:
 - i. Count of dendritic cells as a function of time (14 timepoints) and status (DC1 versus DC2).
 - ii. Count of DC2 as a function of time (14 timepoints) and PDL-1+/- status,
 - iii. Count of macrophages as a function of time (14 timepoints) and status (M1 versus M2)
 - iv. Count of M2 cell as a function of time (14 timepoints) and PDL-1+/- status,
 - v. Count of CD4 T cells as a function of time (14 timepoints) and follicular helper function status.
 - vi. Count of T cells as a function of time (14 timepoints) and activated status (activated versus naïve),
- vii. Count of activated T cells as a function of time (14 timepoints) and PD1+/- status,
- viii. Count of Tregs as a function of time (14 timepoints) and activated status (activated versus resting),
- ix. Count of memory T cells as a function of time (over 14 timepoints) and type of memory cells (effector versus central memory versus terminally differentiated effector memory,
- x. Count of B cells as a function of time (14 timepoints) and activated status (activated versus resting),
- xi. Count of myeloid suppressor cells as a function of time (14 timepoints) and PDL-1+/-status,

For these count variables, Poisson Regression Analysis based on generalized estimating equations (GEE) method will be performed by utilizing the procedure PROC GENMOD SAS 9.4 with Poisson distribution, log link function and independent covariance structure.

Continuous variables such as cytokine levels (GM-CSF, IL-1b, IL-1RA, IL-2, IL-2R, IL-4, IL-5, IL-6, IL-7, IL-8, IL-10, IL-12, IL-13, IL-15, IL-17, TNF alpha; MCP-1, MIP1a, MIP1b, MIG, RANTES, IFN-alpha, IFN-gamma, IP-10, Eotaxin) will be examined over time (14 timepoints) using mixed model repeated measures (MMRM) by utilizing PROC MIXED SAS 9.4. In both of the models to be fit to these immune markers, the status of infection as a time-dependent covariate will be included to examine the effect of both time and infection on cell cytokine levels.

8.3.5 Longitudinal analysis of the gut microbiome.

The time points of stool sample collection are:

- 1) Screening Visit (up to 7 days post consent). If patient signs consent within 7 days of transplant admission, stool sample collection will start from item "2" (Preconditioning)
- 2) Preconditioning (to be collected within 48 hours prior to transplant admission)
- 3) Engraftment, (within 72 hours of ANC > 500)
- 4) Day 1 of Week 1 of combined checkpoint therapy.
- 5) Day 1 of Week 4 of combined checkpoint therapy,
- 6) Day 1 of Week 7 of combined checkpoint therapy,
- 7) Day 1 of Week 12 of combined checkpoint therapy.
- 8) Day 1 of Week 18 of combined checkpoint therapy, and
- 9) Day 1 of Week 26 of combined checkpoint therapy.
- 10) End of Treatment Visit
- 11) Post-transplant, 9 months,
- 12) Post-transplant, 12 months,

Amendment9 09NOV2021 Page 40 of 77

- 13) Post-transplant, 15 months.
- 14) Post-transplant, 18 months and / or
- 15) Relapse, as it occurs.

Counts of specific intestinal microbial strains will be examined overtime (15 time points) using Poisson regression analysis utilizing PROC GENMOD as described in analysis of blood immune markers. In each of the models for each microbial strain, status of infection as a time-dependent covariate will be included as microbial along timepoint variable.

The overall microbial composition will be determined by 16S rRNA miSeq Illumina platform and analyzed by Second Genome Solutions proprietary 16S bioinformatic data analysis software package.

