APPENDIX D: STUDY FLOWCHART

	Screening	Treatment	Safety	End of			
	Phase	cycles	Visits	treatment	P	ost treatmen	t
	Screening (Visit 1)	Day 1 (+/- 2 days) of weeks 1, 4, 7, 10, 12, 14, 16, 18, 20, 22, 24, 26 Week 1 is defined as initiation of checkpoint inhibitors, not weeks post	Day 1 (+/- 2 days) of weeks 2, 3, 5, 6, 8, and 9 Week 1 is defined as initiation of checkpoint inhibitors, not weeks post ASCT.	For study completion or discontinuation of therapy (discon) (To be completed within 2 weeks of last dose) (+/- 14 days)	Safety visit 30 days post End of Treatment Visit (+/- 14 days)	Follow up visits every 12 weeks post End of Treatment Visit (+/- 14 days)	Survival visits every 12 weeks post End of Treatment (+/- 14 days)
		ASCT.	post ASC1.				
		1	Administrativ	e Procedures			
Informed Consent	Xa						
Informed Consent for Future Biomedical Research - Optional	Xn						
Inclusion/Exclusion Criteria	X						
Demographics/Medical History	Xa						
Prior and Concomitant Medication Review	X	Х	Х	X	Х	Xg	
Trial Treatment Administration (See Section 5.0)		х					
Post-study disease status				Х	X	Х	
Survival Status							X ^h
		С	linical Procedu	res/Assessments			
Review Adverse Events	Χ	Х	X	X	X	Xa	
Physical Examination	X d	Х	Х	Х	Х	Х	
Vital Signs and Weight	X d	Х	Х	Х	Χ	Х	
12-Lead Electrocardiogram	Xp						
MUGA or ECHO with	Xp						
Imaging Assessment ^e	X ^{b, e}						
Pulmonary Function Test	Xp						
ECOG PS	Χď	Х		Х	Х	Х	
			Laboratory /	Assessments			
CMV, HIV, HTLV, Hepatitis B, Hepatitis C evaluations	Χď						
Pregnancy Test ^c	X ^d	X		X	Х		
CBC with differential	X ^d	Х	Х	X	Х	Х	

Complete Metabolic Panel (Na, K, BUN, Creatinine, Cl, CO2, Anion Gap, Ca, P, Mg, Uric Acid, Alk Phos, AST, ALT, bilirubin, albumin, LDH, Glucose, GGTP).	Xq	Х	х	х	х	Х	
Total CK	X d	X			Х		
LFTs (PT/INR, aPTT, albumin, total bilirubin)	X^d						
Baseline disease assessments	X ^{d, f}						
Urinalysis	Χď	On weeks 1,7,14,22 and 26 only		Х			
Haptoglobin	X d	On weeks 1, 7, 12, 16, 20, and 24 only			х		
TSH, T3 and free T4; lipase and amylase, cortisol	Χď	On weeks 1,7,14,22 and 26 only		х			
Bone Marrow Biopsy / Tumor Biopsy	X^k			Xk			
Peripheral blood collection for blood immune phenotype and metabolomics analysis	Χ ^L	X On weeks 1, 4, 7, 12, 18 and 26 only				Post transplant months 9, 12,15 and 18 and at time of relapse	
Stool sample for microbiome analysis	Χ ^m	X On weeks 1,4, 7, 12, 18 and 26 only				Post transplant months 9, 12,15 and 18 and at time of relapse	

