- k Tumor Biopsies and/or Bone Marrow Biopsies for Lymphoma subjects (Groups A through D) and Bone Marrow Biopsies for Multiple Myeloma subjects (Groups E & F) will be collected at screening, end of treatment, complete response, and at relapse, if clinically indicated . Tumor Biopsies and/or Bone Marrow Biopsies will be performed to confirm complete response at the discretion of the investigator. For Bone Marrow Biopsies, the research sample will be collected (aspirate, send the first pull, yellow top tube) to [name] lab. Additional samples for all disease groups will be sent to pathology for immunostaining of fixed tissue for PDL1 expression on tumor cells and for the in situ presence of CD4 and CD8 T cells with PD1 expression. If viable biopsy material is unavailable for research purposes, [name] lab will access fixed archival tumor materials for preparing tumor lysates and possibly for retrieving T cell DNA for repertoire analysis. Samples for Georgetown University subjects are to be shipped via Fed Ex on the day of collection tubes banded in sealed plastic bag and wrapped in bubble wrap at room temperature to [name] lab.
- ^L Two time points are to be collected for peripheral blood samples prior to combined checkpoint therapy initiation: 1. During the screening visit; and 2. An apheresis sample from the Apheresis product (1x yellow top tube $-\frac{1}{2}$ full (4mL)). For patients in groups A-E who already had Apheresis product collected, the apheresis sample may be performed on the frozen product. For group F ONLY, apheresis sample will not be collected.
- ^m Three time points are to be collected for stool samples prior to combined checkpoint therapy initiation: 1. Screening Visit (up to 7 days post consent); 2. Preconditioning (to be collected within 48 hours prior to transplant admission); and 3. At engraftment (within 72 hours of ANC ≥ 500). For patients who sign consent within 7 days of transplant admission, the Screening Visit sample will not be collected, and collection will start with the Preconditioning sample.
- ⁿ An optional informed consent for the Hackensack University Medical Center sampling protocol, TMBK 06.05.039, will be presented at time of screening if the subject is not currently participating.

Amendment9 09NOV2021 Page 59 of 77

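### Three of the 14 timepoints in the Section 8.3.4 models are not scheduled blood draws, and separately the cell- and stool-count models treat visits lost after relapse as missing completely at random

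*Combined protocol and SAP*

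**What the plan says.** Section 8.3.4 opens its list with "Longitudinal analysis will be performed on blood samples collected at 14 time points" and then states: "Cell counts in all subsets will be analyzed as repeated measurements obtained at the 14 timepoints to examine the changes over time". It carries that list into the models: "The covariates in this model will be timepoints (14 timepoints listed above) and subset of cell population". The eleven within-subset count models and the cytokine models use the same 14 points. Three entries differ in kind from the rest:

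- **Relapse** is listed as "Relapse, as it occurs". The text accepts that a patient may have fewer points, "or less when time of relapse as the last timepoint".
- **End of Treatment** is set in the Appendix D flowchart at completion or at discontinuation of therapy, within 2 weeks of the last dose and with a 14-day window either way.
- **Apheresis** is described in Appendix D footnote L as "An apheresis sample from the Apheresis product". For patients who consent after collection, "the Apheresis Sample will be performed on the previously collected, frozen product". Group F has no such sample.

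Cell counts are to be fitted by Poisson GEE with log link and independence structure. TCR diversity scores and cytokines use MMRM. Time-dependent infection status is the only further adjustment. No term for relapse status, specimen type or actual day is planned, and no missing-data method is given.

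Section 8.3.5 applies the same Poisson approach to stool counts at 15 points, including End of Treatment and Relapse.

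**The concern.** Two separate problems arise.

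The first is the time variable. Relapse is an event, End of Treatment is a visit whose date depends on how long the patient stayed on therapy, and Apheresis is a different specimen. A contrast between one of these levels and a scheduled draw compares different patients, different dates or different material, so it does not isolate change within patients.

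The second is dropout in the count models. An independence GEE with categorical time essentially compares the means of whoever is present at each level. That estimates change only if absence is completely at random. Here absence after relapse is built in, so months 9 to 18 describe mainly patients who have not relapsed.

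Immune reconstitution is a secondary objective in both phases, and Section 1.0 says that the immune phenotype will be monitored at the time of progression. Either problem could produce an apparent reconstitution trend, or an apparent change at relapse, when no patient has changed.

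**Working it through.** **1. Count of levels.** Screening 1 + apheresis 1 + on-treatment draws 6 (Weeks 1, 4, 7, 12, 18, 26) + End of Treatment 1 + Months 9, 12, 15, 18 (4) + relapse 1 = 14, as the plan states. Scheduled peripheral-blood draws: 14 − 3 = 11. For stool: 15 − 2 (End of Treatment, Relapse) = 13.

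**2. When End of Treatment falls.** Treatment starts 14 to 28 days after stem cell infusion (Section 5.2). Week 26 Day 1 is 25 × 7 = 175 days later, at day 189 to 203.

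- Completers: from day 189 to day 203 + 14 + 14 = 231, overlapping Week 26.
- After one dose only: from day 14 to day 28 + 14 + 14 = 56.

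One label can therefore span 231 − 14 = 217 days, about seven months. Section 5.9 also ends study therapy at progression, so an on-treatment progressor can supply nearly simultaneous samples under two different time labels.

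**3. How many relapse samples.** Section 8.1 gives historical 18-month PFS of 40-50% and a target of 57%. Events by 18 months = n × (1 − PFS):

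- n = 7: 7 × 0.43 = 3.0 to 7 × 0.60 = 4.2
- n = 37: 37 × 0.43 = 15.9 to 37 × 0.60 = 22.2

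These are upper bounds, because Section 8.3.3 counts death from any cause as an event and a death without relapse gives no relapse sample.

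**4. Illustration for the count models, with no true change.** Let p be the share relapsing by month 18, and r the relapsers' mean count relative to non-relapsers. Everyone is present at Week 1, and only non-relapsers at month 18.

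- Week 1 mean = (1 − p) + p × r
- Relapse/Week 1 = r ÷ Week 1 mean
- Month 18/Week 1 = 1 ÷ Week 1 mean

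With p = 0.5:

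| Relapsers lower by (assumed) | Week 1 mean | Relapse/Week 1 | Month 18/Week 1 |
|---|---|---|---|
| 0% | 1.00 | 1.00 | 1.00 |
| 30% | 0.85 | 0.70/0.85 = 0.82 | 1.00/0.85 = 1.18 |
| 50% | 0.75 | 0.50/0.75 = 0.67 | 1.00/0.75 = 1.33 |

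**5. Simulation of the planned count model.** It used Poisson GEE, independence structure, categorical time and no true within-patient change. The assumptions, none from the documents, were a between-patient SD of log count of 0.5 to 0.8 and a relapse hazard ratio (HR) per SD higher count of 1.0, 0.67 or 0.5. The ratios cover 18-month PFS of 40% and 57%. The last column is for 37-patient cohorts with PFS about 40% and SD 0.5.

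| HR per SD | Relapse/Week 1 | Month 18/Week 1 | Relapse contrast p<0.05 |
|---|---|---|---|
| 1.0 | 1.00 | 1.00 | 7-9% of runs |
| 0.67 | 0.78-0.89 | 1.10-1.27 | 13-23% |
| 0.5 | 0.67-0.83 | 1.16-1.41 | 29-31% |

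The apheresis/Week 1 ratio simply returns whatever enrichment is assumed for the product (1, 2 or 5). At 2-fold or more the contrast had p<0.05 in every run.

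**6. Which problem drives which result.** With categorical time, the month 18/Week 1 ratio depends only on who is present at those two visits. Dropping the three unusual levels would leave it at 1.10-1.41 under HR 0.67 to 0.5. The month-18 effect therefore comes from series ending at relapse under independence GEE, not from the list of 14.

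**The case against.** Several points on the other side stand.

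- **MMRM.** A reader might infer that dropout undermines all of Section 8.3.4. The documents do not support that. TCR scores and all cytokines use MMRM, which is valid when dropout depends on observed data. The dropout point and the ratios above apply to cell and stool counts only. MMRM does not cure the time variable: its models still treat a thawed product, a visit without a fixed day and an event as times.
- **Coding of time.** A reader might also infer that the three levels distort every estimated change. The plan does not say how time is coded. If it is categorical, these levels distort their own contrasts and the overall time test, but do not directly shift contrasts among scheduled draws. Only if time is coded 1 to 14 as a trend is the slope affected too.
- **Size.** The relapser deficits are assumed, and with no association between marker and relapse the selection bias is nil. The documents do not say that apheresis counts are on a different scale. That is an inference from the specimen type.
- **Purpose.** Sampling at relapse is a stated objective, so the sample belongs in the trial. Only its place in the time factor is at issue.
- **Continued sampling.** Sections 5.8 and 5.9 keep collecting samples after treatment stops, so early stopping alone does not empty the later visits. Section 8.3.4 nevertheless makes relapse the last point.

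**Conclusion.** The point holds in two parts. In all 8.3.4 models, the Relapse, End of Treatment and Apheresis contrasts and the overall time test mix patient selection or specimen type with change over time, and a 1-14 trend coding would carry this into the slope. The Relapse and End of Treatment levels raise the same issue for stool in 8.3.5. Separately, the cell- and stool-count models rely on visits being missing completely at random although series end at relapse.

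If half the patients relapse and relapsers run 0% to 50% lower, the spurious relapse/Week 1 ratio lies between 1.00 and 0.67, and the month 18/Week 1 ratio between 1.00 and 1.33. These figures show what could happen. They are not expected sizes, because the documents give no marker-relapse association.

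The measures concerned are secondary (blood) and tertiary (stool). The primary safety and PFS endpoints and the expansion and stopping decisions do not use them. The text should be changed before these data are analysed.

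**What to change.** Amend Sections 8.3.4 and 8.3.5 as follows.

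1. In all 8.3.4 models, use as categorical time only the 11 scheduled blood draws: Screening; Weeks 1, 4, 7, 12, 18, 26; Months 9, 12, 15, 18. In 8.3.5, use only the 13 scheduled stool samples.
2. Analyse the relapse sample as a paired within-patient change from the last scheduled pre-relapse sample.
3. Take End of Treatment out of the time factor. Assign an early stopper's sample to the nearest scheduled visit window by actual date if that visit has no sample; otherwise summarise it separately. For completers, use the Week 26 sample.
4. Summarise the apheresis product separately.
5. For cell and stool counts, replace independence GEE with a count mixed model with a patient random effect, or with weighted GEE, either being valid when dropout depends on observed data. Keep MMRM for TCR scores and cytokines.

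Steps 1 to 4 remove the mixing of labels and specimens. Step 5 is needed as well, because they leave the selection at months 9 to 18 in place. The cost is SAP wording, some extra programming and an explicit modelling assumption about dropout. All the samples are already collected under the plan.
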